DOC, defined as 2^{0/7} gestational weeks, will be calculated as first day of LMP plus 14 days (2 weeks).

If EDD is not reported by the HCP but LMP data are available, the registry will use first day of LMP to calculate EDD, gestational age, and DOC.

Individuals will be considered exposed during pregnancy if the exposure occurs any time from 25 days prior to the DOC to the pregnancy outcome. For the analysis of MCM, first trimester exposure will be defined as exposure from 5 times the product's half-life (i.e., 25 days for tirzepatide) prior to the DOC to 13^{6/7} gestational weeks.

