To estimate the number of pregnant individuals who will need to be enrolled to result in 265 live births per cohort, several factors were considered, including the expected registry live birth rate, the proportion of enrolled individuals expected to be exposed to tirzepatide in the first trimester, and the proportion of enrolled individuals expected to be excluded from the analysis population. It was assumed that 90% of enrolled individuals would be exposed in the first trimester, 90% of enrolled pregnancies would result in a live birth,^{72,73} and 10% of enrolled individuals would be excluded from the analysis population due to the occurrence of pregnancy outcome prior to enrollment (retrospectively enrolled participants), exposure to a known teratogen or an investigational medication or congenital infectious agents during pregnancy (teratogen/investigational medication/congenital infectious agent-exposed participants), lack of pregnancy outcome data (participants lost to follow-up; assumed to constitute 5%), or inclusion of a prior pregnancy in the analysis population (subsequent pregnancies). These assumptions are based on experience with other similar study designs. To ensure adequate sample size in the main analysis population is achieved, enrollment of the main analysis population will be assessed throughout data collection. If higher than anticipated percentages of participants would be excluded from the analysis population, it will be assessed what (if any) potential mitigations should be implemented. It is also acknowledged that there could be some effective sample size loss due to the use of stabilized IPTW. The extent and potential mitigations for this will be assessed after approximately 100 participants have enrolled in each of the cohorts.

Given these assumptions, to attain 265 live births per cohort, 364 (=265/0.9/0.9/0.9) pregnant individuals would need to be enrolled in each of the three cohorts of the study population, and a

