9.11.2.1. Analysis of Primary Outcome

Prevalence of the primary outcome will be calculated according to the conventions described in [Table 9.6](#). In general, prevalence will be calculated by dividing the number of cases with an MCM by the appropriate denominator. Prevalence is preferred over incidence when examining pregnancy outcomes, such as congenital malformations, because incidence cannot be reliably estimated given the complexities in the reproductive process.⁹⁷

For MCM, prevalence in the exposed cohort will be calculated among the subset of individuals who are exposed during the first trimester. For the primary analysis, prevalence will be calculated among live births, and a secondary analysis will be conducted among live births and fetal losses ([Table 9.6](#)).

The unweighted univariate regression will be used to compare the crude (unadjusted) relative risks (RRs) of MCM in the tirzepatide exposed and each of the comparator groups, respectively: tirzepatide exposed vs. AOM active comparator and tirzepatide exposed vs. AOM unexposed comparator.

Adjusted methods will incorporate weights estimated using the inverse probability of treatment weighting (IPTW) method to balance the cohorts regarding observable covariates. A weighted generalized linear model using a binomial family and a log (RR) link with robust sandwich variance estimation or a modified Poisson regression⁹⁸ with robust error variance will be employed to estimate an adjusted RR. As with the unweighted analysis, two sets of comparisons will be conducted separately: tirzepatide vs. AOM active comparator and tirzepatide vs. AOM unexposed comparator.

The adjusted comparison of the overall prevalence of MCM observed in the tirzepatide exposed and the comparator cohorts will be considered the primary analysis. A p-value <0.05 will be considered statistically significant.

Table 9.6. Calculation of Primary Outcome Prevalence

Outcome	Numerator	Denominator
Primary analysis: among live births	Live births with confirmed (by adjudication) MCMs (excluding MCMs not known to be associated with medication exposure ^a) among individuals with pregnancy outcome data and, if applicable, exposure during 1 st trimester	Live births among individuals with pregnancy outcome data and, if applicable, ^b exposure during 1 st trimester

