Stillbirth [Exposure: Any trimester]	Individuals with pregnancy ending in stillbirth	Individuals included in the analysis population
Sensitivity analysis: Stillbirth	Stillbirths among individuals with pregnancy outcome data	Individuals with pregnancy outcome data
Infant Outcomes		
Minor congenital malformations [Exposure: Any Trimester]	Live births with minor congenital malformations among individuals with pregnancy outcome data	Live births among individuals with pregnancy outcome data
Preterm birth [Exposure: DOC to < 37 weeks gestation]	Singleton preterm live births without MCMs among individuals with pregnancy outcome data who are enrolled (and exposed, if applicable) prior to 37 gestational weeks	Singleton live births without MCMs among individuals with pregnancy outcome data who are enrolled (and exposed, if applicable) prior to 37 gestational weeks

Outcome [Exposure window]	Numerator	Denominator
SGA [Exposure: Any trimester]	Singleton live births who are SGA at birth among individuals with pregnancy outcome data	Singleton live births among individuals with pregnancy outcome data
Sensitivity analysis: SGA	Singleton live births without MCMs who are SGA at birth among individuals with pregnancy outcome data	Singleton live births without MCMs with weight data among individuals with pregnancy outcome data
Postnatal growth and development outcomes		
Postnatal growth deficiency (at 4 and 12 months) [Exposure: Any trimester]	Singleton infants with postnatal growth deficiency based on weight/length/head circumference among infants with weight/length/head circumference data at the time point	Singleton infants with follow-up data at the time point
Sensitivity analysis: Postnatal growth deficiency (at 4 and 12 months)	Singleton infants without MCMs who were not born preterm or SGA with postnatal growth deficiency based on weight/length/head circumference among infants with weight/length/head circumference data at the time point	Singleton infants without MCMs who were not born preterm or SGA with weight/length/head circumference data at the time point
Infant developmental delay (at 4 and 12 months) [Exposure: Any trimester]	Singleton infants with developmental delay in a particular category among infants with developmental milestone data for the category at the time point	Singleton infants with follow-up data at the time point

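### Minor malformations are analysed with exposure in any trimester and major ones with first-trimester exposure, with no reason given; this may modestly dilute the minor-malformation risk ratio if minor defects arise early

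*Protocol*

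**What the plan says.** Table 9.7 (Section 9.11.2.2) labels the row "Minor congenital malformations [Exposure: Any Trimester", and its denominator is "Live births among individuals with pregnancy outcome data". Neither the numerator nor the denominator carries a condition on when exposure began.

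For MCM the rule differs. Section 9.11.2.1 states: "For MCM, prevalence in the exposed cohort will be calculated among the subset of individuals who are exposed during the first trimester". Table 9.6 repeats the condition in the live-birth analysis and in the analysis of all pregnancy outcomes, and its footnote confines it to exposed cohorts. Section 9.7.5 gives the window, from five half-lives before conception to 13 6/7 weeks, and ties it to one outcome: "For the analysis of MCM, first trimester exposure will be defined as exposure from 5 times".

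Table 9.3 describes both kinds of malformation as present at birth and of prenatal origin, and puts minor malformations through the MCM adjudication process. In that process the evaluators also record roughly when each defect developed.

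Three other places bear on the point:
- Section 9.9.1 assumes that "90% of enrolled individuals would be exposed in the first trimester".
- Section 9.7.1 moves a comparator participant who starts tirzepatide later in pregnancy into the tirzepatide cohort for analysis.
- Section 9.11.2.5 plans subgroup analyses of all outcomes by earliest trimester of exposure, if numbers allow.

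**The concern.** The MCM rule presumes that a first exposure after the first trimester is too late to matter for a major structural defect. If the same holds for minor defects, the any-trimester window brings in exposed pregnancies in which the drug could not have acted on the outcome. These carry background risk and move the RR toward 1, which is the unwelcome direction in a safety study.

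The protocol follows this logic elsewhere in Table 9.7: spontaneous abortion requires exposure before 20 weeks and preterm birth before 37 weeks. Section 9.11.2.7 also worries that a wide pre-conception window could dilute an association. The shorter windows planned there tighten only the early end and do not remove participants first exposed in the second or third trimester.

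A second consequence is that the minor and major malformation estimates come from differently defined exposed groups, so a difference between them is harder to interpret.

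**Working it through.** **The plan's own figures.** For MCM at 3% against 9% (RR 3), two-sided 0.05, 80% power and 1:1 allocation, the Walters approximation to Fisher's exact test gives 265 live births per cohort, as in Table 9.4. Enrolment is 265 / (0.9 × 0.9 × 0.9) = 363.5, rounded up to 364, as in Section 9.9.1. The three factors are first-trimester exposure, live birth ("90% of enrolled pregnancies would result in a live birth") and retention in the analysis population.

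**How many late-exposed live births enter.**
- Any trimester: 364 × 0.9 × 0.9 = 294.8, about 295.
- First trimester only: 364 × 0.9 × 0.9 × 0.9 = 265.4, about 265.
- Difference: about 29 of 295, or 10%.

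**Dilution.** Let f be the share of the exposed group with first-trimester exposure and p the comparator risk. Assume that exposure beginning later has no effect. The exposed risk is f·RR·p + (1 − f)·p, so

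observed RR = f·RR + (1 − f) = 1 + f(RR − 1).

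| f | True RR 3.0 | True RR 2.0 | True RR 1.5 |
|---|---|---|---|
| 0.95 (assumed) | 2.90 | 1.95 | 1.475 |
| 0.90 (Section 9.9.1) | 2.80 | 1.90 | 1.45 |
| 0.80 (assumed) | 2.60 | 1.80 | 1.40 |

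Only the 0.90 row rests on the protocol. The others show sensitivity.

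**Size against sampling error.** Table 9.4 has no row for minor malformations, so a prevalence must be assumed. At 3% and 295 live births per cohort, expected cases are 0.03 × 295 = 8.85 and 0.084 × 295 = 24.78. The standard error of log RR is √(1/24.78 − 1/295 + 1/8.85 − 1/295) = 0.383. The 95% interval around 2.8 is 2.8 × exp(±1.96 × 0.383), about 1.3 to 5.9. A shift of 0.2 is small beside that.

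**Effect of restriction on power** (normal approximation, f = 0.90, prevalences assumed):

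| Assumed prevalence, true RR | Any trimester, 295 vs 295 | First trimester, 265 exposed vs 295 | First trimester, 265 vs 265 |
|---|---|---|---|
| 3%, RR 3 | 81% | 85% | 83% |
| 5%, RR 2 | 56% | 62% | 59% |
| 10%, RR 1.5 | 38% | 44% | 41% |

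Under the dilution assumption, removing late exposures gains slightly more power than the smaller sample loses.

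**The case against.** The strongest reply is that the premise is not in the document. Table 9.3 says only that minor malformations are of prenatal origin, which covers all of gestation. No section says when minor defects form, and the list of minor anomalies is a cited outside source. That stands. A reader might infer that defects formed before the first dose are definitely being scored as exposed and that the RR is definitely diluted. The protocol does not support that without three further conditions: a true effect, susceptible minor defects arising by 13 6/7 weeks, and no effect of later exposure.

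Nor is this a contradiction. Section 9.11.2.2 sets denominators outcome by outcome on clinical grounds, and Section 9.7.5 ties the first-trimester definition to MCM. Shared adjudication does not oblige a shared exposure window. That also stands; what remains is that the difference is unexplained.

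Mitigation exists. The earliest-trimester subgroup would give the first-trimester estimate, and on the plan's figures that stratum is the largest. The recorded timing of defects would show when a counted anomaly preceded the first dose. This stands in part: the subgroup is conditional on sample size, and neither measure alters the main estimate.

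Finally, late-only exposure may be below 10%. Section 7.4.3 says patients are currently advised to discontinue tirzepatide once pregnancy is recognised. A 20% late-only share has no source in the protocol.

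**Conclusion.** The point holds in a limited form. The exposure window for minor malformations differs from that for MCM without explanation. If minor defects arise by the end of the first trimester, the difference may bias the minor-malformation RR modestly toward 1: 3.0 to 2.8, or 2.0 to 1.9, at the protocol's 90%. This assumes that later exposure has no effect and that comparators are at background risk. For the active-comparator contrast, the latter means that the comparator drugs have no effect of their own on these defects.

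A reader might conclude that the two malformation results cannot be read together. That goes too far: on the plan's figures about 90% of the exposed live births are common to both analyses. They are better described as not directly comparable. The outcome is secondary, its p-values are nominal under Section 9.11.2, and the primary MCM analysis is unaffected. This is a desirable tidy-up rather than a necessary correction.

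**What to change.** In the minor-malformation row of Table 9.7, add the first-trimester exposure condition from Table 9.6 to the numerator and denominator for the exposed cohorts, and change the window label to match. Extend the Section 9.7.5 definition so that it covers minor malformations as well as MCM. Keep the any-trimester calculation as a sensitivity row, as Table 9.7 already does for several other outcomes. If the wider window is intended because some minor anomalies are thought to arise later, say so in Section 9.11.2.2 and keep it.

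The cost is a wording change and about 10% fewer exposed live births (roughly 295 to 265) in this one secondary analysis. If later exposure does affect minor defects, the restricted estimate would miss that effect, which is why the any-trimester row should stay.

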Abbreviations: ACOG = American College of Obstetricians and Gynecologists; CDC = Centers for Disease Control and Prevention; EUROCAT = European Registration of Congenital Anomalies and Twins; HCP = healthcare provider; INTERGROWTH-21st = International Fetal and Newborn Growth Consortium for the 21st Century; LGA = large for gestational age; MACDP = Metropolitan Atlanta Congenital Defects Program; MCM = major congenital malformation; RWG = rapid weight gain; SAB = spontaneous abortion; SAC = Scientific Advisory Committee; SGA = small for gestational age; US = United States; WHO = World Health Organization

^a Infants born preterm or SGA will be excluded from these calculations.

^b Equivalent assessments are also accepted (e.g., Munich Functional Developmental Diagnostic- MFED or Bayley's Scale of Infant Development)

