Sensitivity analysis: Infant developmental delay (at 4 and 12 months)	Singleton infants without MCMs who were not born preterm or SGA with developmental delay in a particular category among infants with developmental milestone data for the category at the time point	Singleton infants without MCMs who were not born preterm or SGA with developmental milestone data for the category at the time point
Exploratory outcomes		
Hyperemesis gravidarum [Exposure: Any trimester]	Hyperemesis gravidarum	Individuals included in the analysis population
Inadequate gestational weight gain [Exposure: Any trimester]	Inadequate gestational weight gain	Individuals included in the analysis population
Maternal cardiac disease [Exposure: Any trimester]	Cardiac disease	Individuals included in the analysis population
LGA [Exposure: Any trimester]	Singleton live births at birth who were born LGA among individuals with pregnancy outcome data	Singleton live births among individuals with pregnancy outcome data
Rapid infant weight gain [Exposure: Any trimester]	Singleton live births without MCM who were not born preterm or SGA with rapid weight gain among infants with at least two recorded weight measurements	Singleton infants without MCMs who were not born preterm or SGA with at least two recorded weight measurements

Abbreviations: LGA = large for gestational age; MCM = major congenital malformation; SAB = spontaneous abortion; SGA = small for gestational age

For most outcomes, the analysis population (denominator) will be the number of pregnant individuals, number of pregnant individuals with pregnancy outcome data, the number of live births, or the number of infants with follow-up data at the specified time points, as appropriate; however, for some outcomes, the analysis population (denominator) will be restricted based on certain relevant factors:

- For live birth and infant outcomes (i.e., preterm birth, SGA, LGA, postnatal growth deficiency, rapid infant weight gain, and infant developmental delay), prevalence will be calculated among live births/infants excluding MCMs and multiple gestation pregnancies due to the higher risk of these outcomes among infants in these groups.
- For postnatal growth deficiency, rapid infant weight gain, and infant developmental delay infants born preterm, or SGA will be excluded from the main analysis population (denominator) due to different growth trajectories.

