- For SAB and preterm birth, prevalence will be calculated among the subset of individuals who are enrolled in the registry prior to 20 and 37 gestational weeks, respectively. Additionally, for these time-to-event outcomes, data will be censored at appropriate time points: 20 gestational weeks for SAB and 37 gestational weeks for preterm birth.
- For pregnancy complications prevalence will be calculated according to the following assessment windows:
 - Pregnancy induced hypertension reported for the first time among participants after 20 weeks gestation.
 - Pre-eclampsia/eclampsia reported among participants after 20 weeks of gestation.
 - New-onset gestational diabetes reported among participants at any time during pregnancy
 - Inadequate maternal weight gain reported among participants at any time during pregnancy.
 - HG reported among participants anytime during pregnancy.
- Prevalence will be calculated at multiple time points for postnatal growth deficiency, rapid infant weight gain, and infant developmental delay will be assessed at 4 months (± 2 weeks) and 12 months (± 2 weeks) of infant age. At each time point, prevalence will be calculated among infants with data available for the particular outcome at that time point. If there is no assessment available at 4 and/or 12 months, available data will be evaluated based on the actual time of assessment (e.g., if the infant was measured at 6 months, these data will be compared to the values appropriate for a 6-month-old infant based on the growth charts). However, only development at 4 and 12 months will be reported as study outcomes, results from other time points will be reported in a separate category.

The unweighted univariate regression will be used to compare the crude (unadjusted) RRs for all outcomes. Adjusted methods will incorporate weights estimated using the IPTW method to balance the cohorts with regard to observable covariates (Section 9.11.2.4). A weighted generalized linear model using a binomial family and a log (relative risk) link will be employed to estimate an adjusted relative risk.

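### Postnatal growth deficiency and developmental delay have two conflicting main analyses, SGA and LGA conflict over malformations, and the Table 9.7 main denominators do not require the measurement

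*Protocol*

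**What the plan says.** Section 9.11.2.2 of the Protocol sends the reader to Table 9.7 for the numerator and denominator of every secondary and exploratory outcome.

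- **Growth deficiency and developmental delay, main rows of Table 9.7.** The denominator is "Singleton infants with follow-up data at the time point". There is no MCM, preterm or SGA exclusion. The numerator comes only from infants with the relevant record; for development it reads "Singleton infants with developmental delay in a particular category among infants with developmental milestone data for the category at the time point".
- **Sensitivity row, growth deficiency.** The denominator is "Singleton infants without MCMs who were not born preterm or SGA with weight/length/head circumference data at the time point". The developmental delay row follows the same pattern.
- **Bullets under Table 9.7.** For preterm birth, SGA, LGA and the postnatal outcomes, "prevalence will be calculated among live births/infants excluding MCMs and multiple gestation pregnancies". For growth deficiency, rapid weight gain and developmental delay, "infants born preterm, or SGA will be excluded from the main analysis population (denominator) due to different growth trajectories".
- **Table 9.3, footnote a (Section 9.7.3)**, attached to the same three postnatal outcomes: "Infants born preterm or SGA will be excluded from these calculations".
- **Later bullet on the 4- and 12-month assessments:** "At each time point, prevalence will be calculated among infants with data available for the particular outcome at that time point".
- **SGA and LGA, main rows of Table 9.7.** The denominator is singleton live births with pregnancy outcome data. MCMs are included and birth weight is not required. The SGA sensitivity row removes MCMs and requires weight. LGA has no sensitivity row.

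**The concern.** Two separate matters are at stake.

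**Which population is main.** The text makes main what the table calls sensitivity. Preterm birth and SGA occur after exposure and are listed as secondary outcomes in Section 9.3. Section 7.3.1 reports reduced fetal weight in rats and rabbits, so an effect on growth that runs through birth size is plausible. Restricting to infants who were neither preterm nor SGA removes that route from the comparison. If the label stays open, the choice could be made after outcome data have accrued.

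**What an unmeasured infant counts as.** Where the numerator needs a record and the denominator does not, an infant seen at the time point but not measured stays in the denominator as a non-case. Section 9.7.3 evaluates weight, length and head circumference separately, and each milestone category separately. An infant who was weighed but has no head circumference would therefore count as not deficient for head circumference. This lowers prevalence, which the secondary objective sets out to describe, and shifts the RR when recording differs between cohorts. The sensitivity rows for growth, development and SGA change the population and the measurement rule together, so a difference from the main result could not be assigned to either.

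**Working it through.** **1. Table and text side by side**

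| Outcome | Table 9.7 main row | Text and Table 9.3 footnote a | Result |
|---|---|---|---|
| Growth deficiency, developmental delay: population | All singletons | MCM, preterm and SGA out (footnote: preterm and SGA) | Conflict |
| Same: measurement needed in denominator | No | Yes, by the time-point sentence | Conflict |
| SGA, LGA: MCMs | Included | Excluded | Conflict |
| SGA, LGA: birth weight needed | No | Not addressed | Uncorrected |
| Rapid weight gain | MCM, preterm and SGA out; two weights needed | Same exclusions | Consistent |
| Preterm birth | MCMs out | MCMs out | Consistent |

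**2. The plan's own figures.** Inputs from Section 9.9.1: two-sided alpha 0.05, power 80%, 1:1, RR 3, Fisher's exact test with the Walters approximation. Power = Φ(√(2n)·[asin√(p_high − 1/(2n)) − asin√(p_low + 1/(2n))] − 1.96). The smallest n per cohort is 70 at 10% (SGA, LGA, growth deficiency), 50 at 13% (developmental delay) and 265 at 3% (MCM). All three match Table 9.4, so the sample size is not in question.

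**3. Unmeasured infants kept as non-cases.** Let m be the share of infants in the denominator without the measurement. The Protocol gives no value; 0–30% is assumed. Observed prevalence = p(1 − m); observed RR = true RR × (1 − m_exposed)/(1 − m_comparator).

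- With p = 10% (Table 9.4): 0.10 × 0.90 = 9%, 0.10 × 0.80 = 8%, 0.10 × 0.70 = 7%.
- Equal m in both cohorts: factor 1.00.
- Exposed 30%, comparator 10%: 0.70/0.90 = 0.78.
- Exposed 20%, comparator 10%: 0.80/0.90 = 0.89.
- Exposed 10%, comparator 20%: 0.90/0.80 = 1.125.
- Exposed 10%, comparator 30%: 0.90/0.70 = 1.29.

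**4. Excluding SGA infants.** Comparator SGA is 10% (Table 9.4). Assumed: exposure doubles it to 20%, growth deficiency is 8% in non-SGA infants and 30% or 40% in SGA infants, and there is no direct effect.

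- At 30%: exposed 0.2 × 0.30 + 0.8 × 0.08 = 0.124; comparator 0.1 × 0.30 + 0.9 × 0.08 = 0.102; RR 1.22.
- At 40%: exposed 0.2 × 0.40 + 0.8 × 0.08 = 0.144; comparator 0.1 × 0.40 + 0.9 × 0.08 = 0.112; RR 1.29.
- SGA excluded, either case: 0.08/0.08 = 1.00.
- If exposure instead raises SGA 1.5-fold, the all-infant RR is 1.11 to 1.14; if threefold, 1.43 to 1.57.

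**5. Infants removed by the text rule.** With preterm birth 8.47% and SGA 10% (Table 9.4), independence gives 1 − 0.9153 × 0.90 = 17.6%. Full overlap gives 10% and no overlap 18.5%. Of 265 live births, about 218 remain (216 to 239).

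**The case against.** **The text already requires measurement for postnatal outcomes.** A reader might infer that the plan definitely scores unmeasured infants as normal throughout. It does not. The time-point bullet says "prevalence will be calculated among infants with data available for the particular outcome at that time point", so for growth and development this is a further conflict between table and text. Only for SGA and LGA does the omission stand with nothing to correct it.

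**The restriction has a stated reason.** Different growth trajectories are a fair ground for looking at term, non-SGA infants; that answers a different question. A reader might also infer that the text rule would hide growth effects altogether. That goes too far: SGA and preterm birth are analysed as outcomes in their own right, and Table 9.7 lists both populations for growth and development. What is undecided is which result is the main one.

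**SGA and LGA are not conditioned on preterm birth or SGA.** It is tempting to extend the pathway argument to them, but the second bullet and the footnote cover only the three postnatal outcomes.

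**Missing measurements may be few.** The Infant Outcomes Form asks for all the measurements and milestones, data collection is identical across cohorts (Section 9.6), and Section 9.11.2.8 expects few missing values for critical data points. Against that, Section 9.13 says that data reflect routine practice without mandatory assessments, and Section 9.8 collects size at pregnancy outcome only when available. The objection limits the likely size; it does not justify the mismatch.

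**Only secondary and exploratory outcomes are touched**, and Section 9.11.2 calls their p-values nominal. This stands and sets the weight of the point.

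**Conclusion.** The contradiction is real and should be fixed before analysis. It is not detail left for the SAP: the Protocol fixes both versions, and an SAP can follow only one. For growth deficiency and developmental delay the main population and the denominator rule are each stated in two incompatible ways, and one version conditions on post-exposure outcomes. For SGA and LGA the treatment of MCMs conflicts, and birth weight is not required in the main denominator.

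The sizes in steps 3 and 4 of the working are illustrations. They rest on assumed shares of unmeasured infants, assumed deficiency rates by SGA status, an assumed effect of exposure on SGA, and no direct effect. With equal missingness the RR does not move, although prevalence is still understated. A reader might infer that the primary result or the power is compromised. The documents do not support that: the MCM analysis has its own denominator in Table 9.6, and the Table 9.4 figures reproduce exactly.

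**What to change.** 1. For growth deficiency, developmental delay, SGA and LGA, keep the Table 9.7 singleton population as the main analysis: no MCM exclusion, and for the two postnatal outcomes no preterm or SGA exclusion. Keep the restricted set as sensitivity. Add an LGA sensitivity row if one is wanted; none exists now.
2. Change the Table 9.7 main denominators to infants with the specific measurement or milestone record at that time point, in line with the existing time-point sentence, and to live births with birth weight for SGA and LGA. State that this removes the bias only if missingness is unrelated to the outcome within cohort.
3. Amend the first two bullets under Table 9.7 and footnote a of Table 9.3 for these four outcomes only. Leave the rules for rapid infant weight gain and preterm birth, and the multiple-gestation exclusion, as they are. Deleting the wording outright would put those consistent rules in conflict with their own table rows.

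The cost is a wording change and slightly smaller denominators than the current table gives. Apart from an optional LGA row, no new analysis or data collection is needed.
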